## **10. ADVERSE EVENTS, SERIOUS ADVERSE EVENTS AND REPORTING**

### **10.1. Adverse Events**

All observed or volunteered AEs regardless of treatment group or suspected causal relationship to the investigational product(s) will be reported as described in the following sections.

For all AEs, the investigator must pursue and obtain information adequate both to determine the outcome of the AE and to assess whether it meets the criteria for classification as a serious adverse event (SAE) requiring immediate notification to Pfizer or its designated representative. For all AEs, sufficient information should be obtained by the investigator to determine the causality of the AE. The investigator is required to assess causality.

Follow-up by the investigator may be required until the event or its sequelae resolve or stabilize at a level acceptable to the investigator, and Pfizer concurs with that assessment.

As part of ongoing safety reviews conducted by the sponsor, any nonserious AE that is determined by the sponsor to be serious will be reported by the sponsor as an SAE. To assist in the determination of case seriousness, further information may be requested from the investigator to provide clarity and understanding of the event in the context of the clinical study.

#### **10.1.1. Reporting Period**

For SAEs, the active reporting period to Pfizer or its designated representative begins from the time that the subject provides informed consent, which is obtained prior to the subject's participation in the study, ie, prior to undergoing any study-related procedure and/or receiving investigational product, through and including 28 calendar days after the last administration of the investigational product. SAEs occurring to a subject after the active reporting period has ended should be reported to the sponsor if the investigator becomes aware of them; at a minimum, all SAEs that the investigator believes have at least a reasonable possibility of being related to investigational product are to be reported to the sponsor.

AEs (serious and non-serious) should be recorded on the case report form (CRF) from the time the subject has taken at least 1 dose of investigational product through the subject's last visit.

#### **10.1.2. Definition of an Adverse Event**

An AE is any untoward medical occurrence in a clinical investigation subject administered a product or medical device; the event need not necessarily have a causal relationship with the treatment or usage. Examples of AEs include but are not limited to:

- Abnormal test findings;
- Clinically significant symptoms and signs;
- Changes in physical examination findings;
- Hypersensitivity;
- Drug abuse;
- Drug dependency.

Additionally, they may include the signs or symptoms resulting from:

- Drug overdose;
- Drug withdrawal;
- Drug misuse;
- Drug interactions;
- Extravasation;
- Exposure during pregnancy (EDP);
- Exposure via breastfeeding;

- Medication error;
- Occupational exposure.
- Worsening of signs and symptoms of the malignancy under study should be reported as AEs in the appropriate section of the CRF. Disease progression assessed by measurement of malignant lesions on radiographs or other methods should not be reported as AEs.

### **10.2. Medication Errors**

Medication errors may result, in this study, from the administration or consumption of the wrong product, by the wrong subject, at the wrong time, or at the wrong dosage strength. Such medication errors occurring to a study participant are to be captured on the medication error CRF, which is a specific version of the AE page, and on the SAE form when appropriate. In the event of medication dosing error, the sponsor should be notified immediately.

Medication errors are reportable irrespective of the presence of an associated AE/SAE, including:

- Medication errors involving subject exposure to the investigational product;
- Potential medication errors or uses outside of what is foreseen in the protocol that do or do not involve the participating subject.

Whether or not the medication error is accompanied by an AE, as determined by the investigator, the medication error is captured on the medication error version of the AE page and, if applicable, any associated AE(s) are captured on an AE CRF page.

### **10.3. Abnormal Test Findings**

The criteria for determining whether an abnormal objective test finding should be reported as an AE are as follows:

- Test result is associated with accompanying symptoms; and/or
- Test result requires additional diagnostic testing or medical/surgical intervention; and/or
- Test result leads to a change in study dosing or discontinuation from the study, significant additional concomitant drug treatment, or other therapy; and/or
- Test result is considered to be an AE by the investigator or sponsor.

Merely repeating an abnormal test, in the absence of any of the above conditions, does not constitute an AE. Any abnormal test result that is determined to be an error does not require reporting as an AE.

### **10.4. Serious Adverse Events**

A serious adverse event is any untoward medical occurrence at any dose that:

- Results in death;

- Is life-threatening (immediate risk of death);
- Requires inpatient hospitalization or prolongation of existing hospitalization;
- Results in persistent or significant disability/incapacity (substantial disruption of the ability to conduct normal life functions);
- Results in congenital anomaly/birth defect;
- Progression of the malignancy under study (including signs and symptoms of progression) should not be reported as an SAE unless the outcome is fatal within the safety reporting period. Hospitalization due to signs and symptoms of disease progression should not be reported as an SAE. If the malignancy has a fatal outcome during the study or within the safety reporting period, then the event leading to death must be recorded as an AE and as an SAE with Common Terminology Criteria for Adverse Events (CTCAE) Grade 5 (see the section on [Severity Assessment](#)).

Medical and scientific judgment is exercised in determining whether an event is an important medical event. An important medical event may not be immediately life-threatening and/or result in death or hospitalization. However, if it is determined that the event may jeopardize the subject or may require intervention to prevent one of the other AE outcomes, the important medical event should be reported as serious.

Examples of such events are intensive treatment in an emergency room or at home for allergic bronchospasm; blood dyscrasias or convulsions that do not result in hospitalization; or development of drug dependency or drug abuse.

Medical device complaints may meet the SAE reporting requirement criteria (see the section on [Sponsor's Reporting Requirements to Regulatory Authorities](#)). An incident is any malfunction (ie, the failure of a device to meet its performance specifications or to perform as intended; performance specifications include all claims made in the labeling for the device) that, directly or indirectly, might lead to or might have led to the death of a subject, or user, or of other persons, or to a serious deterioration in their state of health.

- A life-threatening illness, even if temporary in nature;
- A permanent impairment of a body function or permanent damage to a body structure;
- A condition necessitating medical or surgical intervention to prevent the above 2 bulleted items;
- Any indirect harm as a consequence of an incorrect diagnostic or in vitro diagnostic device test results when used within the manufacturer's instructions for use;
- Fetal distress, fetal death, or any congenital abnormality or birth defects.

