**Figure 1. Chemical Structure of Dalteparin Sodium**

### 3.2. Rationale

Dalteparin sodium (Fragmin®) is a low molecular weight heparin (LMWH), produced by degradation of heparin, a member of the glycosaminoglycan (GAG) family of biological entities found in the intestinal mucosa. Dalteparin was first approved in the US in December 1994 for primary prophylaxis of DVT in subjects undergoing abdominal surgery. This was followed by approvals for primary prophylaxis of DVT in subjects undergoing hip surgery and in medical subjects with severely restricted mobility during acute illness. Dalteparin sodium is also indicated for the prophylaxis of ischemic complications in unstable angina and non-Q-wave myocardial infarction, when concurrently administered with aspirin therapy.

Dalteparin was approved in 2006 for the extended treatment of VTE in adult patients (age  $\geq 18$  years) with cancer. For these indications, dalteparin has an acceptable safety profile. Further information regarding dosage, safety profile, etc., can be found in the current US Package Insert or local Summary of Product Characteristics, which will serve as the Investigators' Brochure for this study.

Multiple retrospective studies have shown that cancer-associated thrombosis (CAT) is a significant entity previously under recognized and under treated. When compared to subjects without cancer, cancer subjects are far more prone to develop VTE; in fact, VTE may represent the initial presenting finding for an otherwise occult cancer. When compared to cancer-free subjects with symptomatic VTE, cancer subjects with VTE are more prone to recurrence and to treatment-related bleeding complications.

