#### **10.4.1. Protocol-Specified Serious Adverse Events**

There are no protocol-specified SAEs in this study. All SAEs will be reported by the investigator as described in previous sections, and will be handled as SAEs in the safety database (see the section on [Serious Adverse Event Reporting Requirements](#)).

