## **13. DATA MONITORING COMMITTEE**

This study will not use a data monitoring committee.

It should be emphasized that the subject, the subject's parent and/or legal representative are at liberty to withdraw their consent to participate at any time, without penalty or loss of benefits to which the subject is otherwise entitled. Subjects, their parents and/or legal representatives, who refuse to give, or withdraw, written informed consent may not be included or continued in this study, but this will not impact their subsequent care.

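### Section 10.4's exemption for malignancy progression does not exclude bleeding or thrombosis, so in children with cancer a serious bleed or clot attributed to progression can lose SAE status and 24-hour notification

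*Protocol*

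**What the plan says.** Protocol section 10.4 lists the usual seriousness criteria and then adds an exemption: "Progression of the malignancy under study (including signs and symptoms of progression) should not be reported as an SAE unless the outcome is fatal". To count, the death must fall inside the time window for safety reports. The next sentence extends the exemption to admissions: "Hospitalization due to signs and symptoms of disease progression should not be reported as an SAE". Neither sentence mentions bleeding or thrombosis, and neither depends on whether the study drug may have contributed.

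Section 10.4.1 adds no list of events that must always be reported as serious: "There are no protocol-specified SAEs in this study".

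Section 10.1.2 keeps the exempted events in the AE record: "Worsening of signs and symptoms of the malignancy under study should be reported as AEs in the appropriate section of the CRF".

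Section 10.12.1 attaches the 24-hour notification of the sponsor to SAEs. Section 13 states: "This study will not use a data monitoring committee".

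**The concern.** An exemption for disease progression makes sense where the malignancy is the condition being treated. Here the condition being treated is VTE, the children may or may not have cancer, and the drug is an anticoagulant. The events that matter most for its safety and efficacy are bleeding and new or progressive thrombosis. A bleed into a tumour, or a new clot in a child whose cancer is advancing, is an event that an investigator could reasonably put down to the malignancy. The exemption as worded then directs that it not be filed as an SAE, even when it leads to admission.

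Two things are at stake. The first is speed: without SAE status there is no stated deadline for the sponsor to learn of a serious event, and no data monitoring committee is in place. The second is consistency: the same hospitalised event would be an SAE in a child without cancer and might not be in a child with cancer, although both enter the same safety summaries.

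**Working it through.** The plan states no figure on this point and no arithmetic applies. The check follows one event through the rules: a non-fatal bleed or new clot on dalteparin that leads to hospital admission.

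| Step | Child without cancer | Child with cancer, event attributed to progression |
|---|---|---|
| Seriousness criterion met (10.4) | Yes, hospitalisation | Yes, hospitalisation |
| Progression exemption (10.4) | Cannot apply | Applies as worded |
| Always-reportable list (10.4.1) | None | None |
| SAE and 24-hour notice (10.12.1) | Required | Not required under the exemption |
| AE entry on the CRF (10.1.1, 10.1.2) | Yes | Yes |
| Unscheduled Event visit (Table 1 notes, 9.3.6) | Yes | Yes |
| Bleeding or VTE endpoint assessment (12.3.5, 12.3.6; SAP 6.1.2.1, 6.3.1) | Yes, by investigator assessment | Yes, by investigator assessment |

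The two columns differ only in the exemption and the SAE row. The event stays in the data, but its seriousness classification and expedited notice can be lost.

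Next, can another provision restore SAE status?

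1. **Important medical events (10.4).** If an event may jeopardise the subject, or may need intervention to avert a serious outcome, "the important medical event should be reported as serious". This rests on medical judgement. It does not name bleeding or thrombosis, and it does not say that it overrides the exemption.
2. **Sponsor upgrade (10.1).** The sponsor may reclassify a nonserious AE as serious during its safety reviews. This works only once the sponsor has seen the AE, and no deadline is stated for AE entry.
3. **Causality (10.7).** Unknown causality is handled as related for reporting purposes. That concerns relatedness, not seriousness, so it does not undo the exemption.
4. **Site contacts.** Unscheduled Event visits and the weekly telephone calls (9.1.9) bring the event to the site's attention. Neither section requires the sponsor to be notified.
5. **Monitoring (15.1).** Visits occur about every 6 to 8 weeks. The contact between visits is said to follow study progress, including subject disposition and the occurrence of SAEs; an event not classed as an SAE is not named among its topics.

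The first two are real routes back, but both are discretionary and the second may be late. None is a rule that guarantees expedited reporting.

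Last, where would the difference appear in the analysis? Protocol section 12.3.6 summarises adverse events by seriousness, among other breakdowns, in the safety population, which pools children with and without cancer. Exempted events would count there as nonserious.

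Endpoint capture needs one qualification. In section 9.1.2, limb (c) of major bleeding covers only transfused bleeds judged unrelated to the underlying condition. A tumour-related transfused bleed that meets no other limb would therefore not be a major bleed. Limbs (a), (b), (d) and (e) carry no such condition.

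**The case against.** The strongest reply is that this is a wording ambiguity with limited consequences. The exemption speaks of progression of the malignancy, section 10.1.2 ties disease progression to measurement of malignant lesions, and bleeding and VTE are defined separately in sections 9.1.1 and 9.1.2. Nothing in the protocol classifies a bleed or a clot as a sign of tumour progression. Several routes also keep the event visible, and the attribution on which the concern depends is itself a judgement.

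Much of this stands, and it rules out several stronger readings that a reader might infer:

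- **That such events go unreported altogether.** They do not. AE recording, the Unscheduled Event visit and the bleeding and VTE assessments do not depend on SAE status.
- **That nothing else can restore SAE status.** The important-medical-event clause and the sponsor upgrade both can.
- **That SAE tables by age group would be distorted.** SAP section 6.3.2 lists SAEs by subject and tabulates treatment-emergent AEs by age group, where exempted events remain. Protocol section 12.3.6 does not specify age group for the breakdown by seriousness.
- **That the protocol itself treats an on-study clot as a sign of progression.** Section 3.2 does say "VTE may represent the initial presenting finding for an otherwise occult cancer", but that concerns undiagnosed cancer at presentation. Cancer subjects here already have a diagnosed malignancy under treatment (inclusion criterion 5). The same section describes bleeding in cancer subjects with VTE as related to treatment, which points away from this reading.
- **That the hospitalisation sentence also exempts admissions for VTE progression**, because it says only disease progression. It sits between two sentences about the malignancy, and that is its natural meaning.

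What the reply does not remove is the text itself. The exemption is specific and directive, has no causality condition and no exception for the events that an anticoagulant trial most needs to hear about. The routes around it are general and discretionary.

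**Conclusion.** The point holds as a gap in a reporting rule. In children with cancer only, a serious non-fatal bleed or thromboembolic event that the investigator attributes to progression can lose SAE classification and 24-hour notification without any breach of the protocol. It does not lose AE recording or investigator assessment for the endpoints. AE summaries by seriousness would then apply different ascertainment rules to children with and without cancer.

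This rests on two conditions: the investigator makes that attribution, and neither the important-medical-event clause nor the sponsor upgrade is used in time. The size cannot be stated. If a share p of such events in cancer children were exempted and not recovered, their SAE count would fall by that same share, but the documents give neither p nor any event rate. A reader might be tempted to turn an assumed p into a rate ratio between cancer and non-cancer children. That would only restate the assumption, for a comparison that neither document plans.

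The change is worth making because it protects timely safety information at little cost. The gap does not threaten the primary PD analysis.

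**What to change.** Add to Protocol section 10.4, directly after the hospitalisation sentence: *This exemption does not apply to bleeding or to new, recurrent or progressive thromboembolic events. Any such event that meets a seriousness criterion is reported as an SAE within 24 hours, regardless of its suspected relation to the malignancy.*

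Replace the reference to the malignancy under study with *the underlying malignancy*, since the trial studies VTE in children with and without cancer. Section 10.1.2 uses the same phrase and should be changed with it.

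The cost is a short wording change in an amendment, a reminder to sites, and a few additional SAE reports for events that prove to be driven by the disease. No treatment rule, endpoint or analysis changes.

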#### **10.4.1. Protocol-Specified Serious Adverse Events**

There are no protocol-specified SAEs in this study. All SAEs will be reported by the investigator as described in previous sections, and will be handled as SAEs in the safety database (see the section on [Serious Adverse Event Reporting Requirements](#)).

#### 10.4.2. Potential Cases of Drug-Induced Liver Injury

Abnormal values in aspartate aminotransferase (AST) and/or alanine aminotransferase (ALT) levels concurrent with abnormal elevations in total bilirubin level that meet the criteria outlined below in the absence of other causes of liver injury are considered potential cases of drug-induced liver injury (potential Hy's law cases) and should always be considered important medical events.

The threshold of laboratory abnormalities for a potential case of drug-induced liver injury depends on the subject's individual baseline values and underlying conditions. Subjects who present with the following laboratory abnormalities should be evaluated further to definitively determine the etiology of the abnormal laboratory values:

- Subjects with AST or ALT and total bilirubin baseline values within the normal range who subsequently present with AST or ALT values  $\geq 3$  times the upper limit of normal ( $\times$  ULN) concurrent with a total bilirubin value  $\geq 2 \times$  ULN with no evidence of hemolysis and an alkaline phosphatase value  $\leq 2 \times$  ULN or not available;
- For subjects with preexisting ALT **OR** AST **OR** total bilirubin values above the ULN, the following threshold values should be used in the definition mentioned above:
- For subjects with preexisting AST or ALT baseline values above the normal range: AST or ALT values  $\geq 2$  times the baseline values and  $\geq 3 \times$  ULN, or  $\geq 8 \times$  ULN (whichever is smaller).

Concurrent with

- For subjects with preexisting values of total bilirubin above the normal range: Total bilirubin level increased from baseline by an amount of at least  $1 \times$  ULN **or** if the value reaches  $\geq 3 \times$  ULN (whichever is smaller).

The subject should return to the investigational site and be evaluated as soon as possible, preferably within 48 hours from awareness of the abnormal results. This evaluation should include laboratory tests, detailed history, and physical assessment. For oncology studies, the possibility of hepatic neoplasia (primary or secondary) should be considered.

In addition to repeating measurements of AST and ALT, laboratory tests should include albumin, creatine kinase, total bilirubin, direct and indirect bilirubin, gamma-glutamyl transferase, prothrombin time (PT)/international normalized ratio (INR), and alkaline phosphatase. A detailed history, including relevant information, such as review of ethanol, acetaminophen, recreational drug, and supplement consumption, family history, occupational exposure, sexual history, travel history, history of contact with a jaundiced person, surgery, blood transfusion, history of liver or allergic disease, and work exposure, should be collected. Further testing for acute hepatitis A, B, or C infection and liver imaging (eg, biliary tract) may be warranted. All cases confirmed on repeat testing as meeting the laboratory criteria defined above, with no other cause for Liver Function Test (LFT) abnormalities identified at the time, should be considered potential Hy's law cases irrespective of availability of all the results of the investigations performed to determine etiology of the abnormal LFTs. Such potential Hy's law cases should be reported as SAEs.

## 10.5. Hospitalization

Hospitalization is defined as any initial admission (even less than 24 hours) in a hospital or equivalent healthcare facility or any prolongation of an existing admission. Admission also includes transfer within the hospital to an acute/intensive care unit (eg, from the psychiatric wing to a medical floor, medical floor to a coronary care unit, or neurological floor to a tuberculosis unit). An emergency room visit does not necessarily constitute a hospitalization; however, the event leading to the emergency room visit should be assessed for medical importance.

Hospitalization does not include the following:

- Rehabilitation facilities;
- Hospice facilities;
- Respite care (eg, caregiver relief);
- Skilled nursing facilities;
- Nursing homes;
- Same-day surgeries (as outpatient/same-day/ambulatory procedures).

Hospitalization or prolongation of hospitalization in the absence of a precipitating, clinical AE is not in itself an SAE. Examples include:

- Admission for treatment of a preexisting condition not associated with the development of a new AE or with a worsening of the preexisting condition (eg, for workup of persistent pretreatment laboratory abnormality);
- Social admission (eg, subject has no place to sleep);
- Administrative admission (eg, for yearly physical examination);
- Protocol-specified admission during a study (eg, for a procedure required by the study protocol);
- Optional admission not associated with a precipitating clinical AE (eg, for elective cosmetic surgery);
- Hospitalization for observation without a medical AE;
- Preplanned treatments or surgical procedures. These should be noted in the baseline documentation for the entire protocol and/or for the individual subject;
- Admission exclusively for the administration of blood products.

Diagnostic and therapeutic noninvasive and invasive procedures, such as surgery, should not be reported as AEs. However, the medical condition for which the procedure was performed should be reported if it meets the definition of an AE. For example, an acute appendicitis that begins during the AE reporting period should be reported as the AE, and the resulting appendectomy should be recorded as treatment of the AE.

